6.1.Primary objective: To evaluate the feasibility of the parallel experimental design, the willingness to participate of eligible patients, and the outcome measures for conducting a randomized phase III clinical experiment comparing partial myometrial resection with hysterectomy in patients with PAS, carried out in 3 different centers, including Fundación Valle del Lili, in a period of 24 months.

6.2.Specific objectives:

- 1. To measure the proportion of eligible patients who agree to participate in this comparison.
- 2. To measure the percentage of screening failure.
- 3. To describe the confirmation of the presence or absence of placental accretenotic spectrum in each case.
- 4. To identify the degree of variability between the different methods of measuring intraoperative bleeding in each of the techniques.

6.3.Secondary objectives:

- 1. Clinical and sociodemographic characterization of the patient.
- 2. To identify the characteristics of the patient's current pregnancy.
- 3. To describe the clinical outcomes of interest in patients randomized to hysterectomy or partial myometrial resection.
- 4. To categorize the severity of surgical complications according to the Clavien Dindo classification.

7. Hypothesis

7.1.Primary hypothesis: It is possible to recruit, randomize, operate and follow-up patients recruited for an experiment comparing two surgical techniques in PAS (Hysterectomy Vs Partial myometrial resection) in a period of 24 months or less.

8. Outcomes measures/endpoints:

8.1.Primary endpoints:

- Proportion of eligible patients who agree to participate in the study.
- Screening failure percentage
- Percentage of patients assigned to each arm of the study.
- Percentage of patients with crossover between assigned study arms.
- Number of subjects who complete follow-up at 42 days postpartum.

8.2. Secondary endpoints:

- Maternal death
- Intra-surgical bleeding volume measured in mL.
- Blood component transfusion requirement, median transfusion of red blood cell units (RBCU)
- Compliance with at least one WHO Near Miss criterion (See Appendix 1)
- Ureteral injuries.
- Bladder injuries
- Need for surgical reoperation.
- Admission to the Intensive Care Unit.
- Days of post-operative hospital stay.
- Use of uterine tamponade with hydrostatic balloons.
- Presence of supra fascial hematoma
- Presence of postoperative ileus
- Vital status of the newborn
- Weight of the newborn

9. Methods:

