9.1.**Study design:** Feasibility study of a randomized, controlled, multicenter clinical experiment on the use of partial myometrial resection vs hysterectomy.

It is expected to have the participation of 2 institutions invited and led by:

Hospital Universitario CEMIC (Buenos Aires, Argentina)- [name] [name].

[name] General Hospital, Universitas Airlangga, (Surabaya, Indonesia)- [name] [name]

The 3 institutions will use the same protocol (they will apply the same surgical technique and carry out the same information recording activities), but the randomization will be stratified for each site to ensure the same number of participants for each arm of the study at the 3 sites.

9.2.**Study population**: Pregnant women with a prenatal ultrasound or magnetic resonance diagnosis of PAS (See Appendix 2: Definition of a suspected case of PAS), who will be taken to surgery to treat this disease at Fundación Valle del Lili and the institutions invited to participate

9.3.Study groups:

- Patients with a confirmed PAS diagnosis (See Appendix 2, Definition of confirmed PAS case) who will undergo partial myometrial resection.

Although it has been reported that this type of surgery is viable in case of involvement of the anterior portion of the uterus, with a healthy myometrium of at least 2cm cephalad to the cervix. Our study suggests that partial myometrial resection should be attempted in all patients randomized to this intervention. Partial myometrial resection may not be feasible in some cases and the patient will receive a hysterectomy. The attempted partial myometrial resection does not imply a greater risk of bleeding for the patient, since having previously performed the vesicouterine dissection, vascular control techniques are readily available that can be applied in the event that the myometrial resection is unsuccessful, and a hysterectomy can be performed without exposing the patient to an increased risk of bleeding.

- Patients with a confirmed diagnosis of PAS (See Appendix 2, Definition of a confirmed PAS case) who will undergo hysterectomy. All patients randomized to this intervention will receive a hysterectomy, regardless of the extent or severity of injury found at laparotomy.

Both groups of patients will receive standard postoperative care (monitoring and hemodynamic, respiratory, metabolic support and in general the management described for this intervention)

9.4.Selection of participants:

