If the diagnosis of PAS is ruled out (If the clinical criteria for PAS proposed by FIGO [Appendix 2] are not present), the patient is excluded from the study and subsequent surgical management will be defined by the treating surgical group.

If the diagnosis of PAS is confirmed by observing the clinical criteria endorsed by FIGO (Appendix 2), the patient's participation in the study is confirmed and the surgical procedure defined by randomization is continued, that is, one of the two arms of the study:

Primary hysterectomy: An incision will be made above the level of the placenta, delivering the newborn. Uterotonics will be administered, and spontaneous delivery of the placenta will be awaited using gentle traction. The absence of spontaneous separation of the placenta will confirm the diagnosis of PAS, the patient will undergo hysterectomy. The complete removal of the uterus will be attempted, including the cervix, the duration of the intervention and intraoperative blood loss will be recorded, as well as the damage to organs neighboring the uterus. In this arm of the study, hysterectomy will be performed in 100% of patients.

Partial myometrial resection: The technique described by Palacios-Jaraquemada et al⁵. will be followed. Briefly, the uterus will be dissected to free it from the posterior wall of

the bladder to the cervix. The vesico-uterine vessels will be ligated and the parametrial space will be visualized. The hysterotomy will be performed in the upper segment, immediately above the area of invasion of the myometrium. The entire invaded myometrium and the entire placenta will be removed. The uterus will repair itself in one or two layers. Intrauterine balloon tamponade will be used if indicated.

Post-operative care will be routine care according to the indication of the treating medical team.

To consult the detailed description of the interventions (hysterectomy and partial resection) and the procedures for the evaluation of clinical outcomes, see the standardized operating plan (See Appendix 4)

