From the admission of the patient to the obstetric care unit until the end of the study follow-up process (42 days after the cesarean section), it will be evaluated whether the patient meets the criteria for extreme maternal morbidity (Consult the maternal morbidity surveillance protocol Extrema Cod: 549 of the National Institute of Health, available at: https://www.ins.gov.co/buscador-eventos/Paginas/Fichas-y-Protocolos.aspx) in case of meeting any of the inclusion criteria, the treating medical team will be in charge of filling out the individual notification form Cod. INS 549 for immediate reporting

In the same way, in the event of the death of a participant during the study period, due diligence of the individual notification form will be carried out for the maternal mortality event, INS Code 551 by the treating medical team.

9.12. Randomization:

There will be a randomization in a 1: 1 ratio in blocks of 4 and 6, stratified by each center. This process will be conducted by a statistician from the Fundación Valle del Lili Clinical Research Center independent of the research group, who will use a public access package: *Random Allocation Software* (http://www.msaghaei.com/Softwares/dnld/RA .zip) for that purpose.

The randomization sequence will rest in the *RED Cap*® software. Prior to the start of the surgical procedure, the clinical coordinator of the study will be asked to reveal the result of the randomization, once the presence of PAS is confirmed (See Appendix 2, confirmed case of PAS), the surgery will continue towards one of the two possible options (hysterectomy or partial myometrial resection). Participants and researchers will be informed of the intervention since it is an open-label clinical experiment.

9.13. Blinding:

This is an unblinded study as it is not possible to conceal the surgical procedure for each arm from the operator (Treating Physician) or from the participant.

The information of each patient will be consigned in electronic formats. In these, the therapeutic modality will not be expressly identified, in such a way that the independent statistician who will perform the analysis will also, in principle, not know the group to which each patient was assigned.

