- **10.2.1. Intraoperative**: The total intraoperative bleeding volume will be measured, type of anesthesia used, type of skin incision, type of uterine incision, FIGO PAS classification, use of interventional radiology, use of intraoperative cell saver ("cell saver"), duration of surgery, use of uterine tamponade with hydrostatic balloons, gender and weight of the newborn.
- 10.2.2. **Immediate post-operatory time**: defined as the first 48 to 72 hours after the intervention, in this period of time, the patient will be monitored in the obstetric gynecological service, where each of the secondary outcomes described will be evaluated: Maternal death, Presence of Near Miss criteria, frequency and volume of transfusion of blood components, bladder injury, ureteral injury, need for reoperation, admission to ICU, days of postoperative hospital stay, disseminated intravascular coagulation, hypovolemic shock, metabolic acidosis, urinary retention, femoral thrombosis, post-operative ileus, supra fascial hematoma.
- 10.2.3. **Medical appointment between 7 and 12 days:** The patient is clinically evaluated by outpatient consultation on-site or telemedicine with the treating physician who determines if any of the secondary outcomes described above have occurred and additionally if she has developed an infection of the surgical wound.
- 10.2.4. **Follow-up at 42 days postpartum:** the patient will be followed up by telephone when she reaches 42 days after the surgical intervention, where a general evaluation of her health will be made, and the follow-up will be terminated.

10.3.Data quality monitoring:

Both the executing institution and the institutions participating in the study will designate a person in charge of monitoring the quality of the data. In the executing institution, the person in charge will be [name], who will perform a data quality analysis of 100% of the data corresponding to the primary outcome to be evaluated and 100% for the secondary outcomes, in this analysis of quality, a review of the data entered into the system will be carried out and it will be compared with the clinical records of each institution, the process will be carried permanent and will be programed the first monitoring with each center 5 days after to first participant enrollment, the additional monitoring visits will be performed according to recruitment rate and presence of primary and secondary outcomes in participating individuals.

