18. APPENDIX

Appendix 1: Near Miss Criteria

Clinical criteria				
Acute cyanosis	Loss of consciousness lasting ≥ 12			
Gasping	hours			
Respiratory rate >40 or <6/min	Loss of consciousness AND absence of pulse/heart beat			
Shock	Stroke			
Oliguria non-responsive to fluids or diuretics	Uncontrollable fit/total paralysis			
Clotting failure	Jaundice in the presence of pre- eclampsia			
Laboratory-based criteria				
Oxygen saturation <90% for ≥60 minutes	Acute thrombocytopenia (<50 000 platelets)			
pH <7.1	Bilirubin>100 mmol/l or > 6.0 mg/dl			
PaO2/FiO2 <200 mmHg	Loss of consciousness AND the			
Lactate >5 mmol/l	presence of glucose and ketoacids in urine			
Creatinine ≥300 mmol/l or ≥3.5 mg/dl				
Management-based criteria				
Use of continuous vasoactive drugs	Dialysis for acute renal failure			
Intubation and ventilation for ≥60 minutes not related to anaesthesia	Transfusion of ≥5 units red cell transfusion Cardio-pulmonary			
Hysterectomy following infection or haemorrhage	resuscitation (CPR)			

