 - a. To perform laparotomy and before performing hysterotomy (opening the uterus), confirm the presence of clinical signs of PAS on the anterior surface of the uterus. The presence of the signs described by the consensus of the International Federation of Gynecology and Obstetrics (FIGO), described in Appendix 2, will be sought. Definition of confirmed case.
 - b. If the presence of clinical signs of PAS is confirmed, the patient continues in the study and the surgical procedure previously defined by the randomization process will be performed.
 - c. If the presence of clinical signs of PAS is ruled out, the patient is excluded from the study and subsequent surgical management will be defined by the group of treating surgeons.
- 9. Apply the selected surgical technique in the randomization process (hysterectomy or partial myometrial resection)

A. Total abdominal hysterectomy: An incision will be made above the level of the placenta, extracting the newborn. Uterotonics will be administered and spontaneous delivery of the placenta will be awaited using gentle traction. The absence of spontaneous separation of the placenta will confirm the diagnosis of PAS, the patient will undergo hysterectomy. The complete removal of the uterus will be attempted, including the cervix, the duration of the intervention and intraoperative blood loss will be recorded, as well as the injury to organs neighboring the uterus. In this arm of the study, hysterectomy will be performed in 100% of patients.

B. Partial myometrial resection: The technique described by Palacios-Jaraquemada et al.5 will be followed. Briefly, the uterus will be dissected to free it from the posterior wall of the bladder to the cervix. The vesico-uterine vessels will be ligated and the parametrial space will be visualized. The hysterotomy will be performed in the upper segment, immediately above the area of invasion of the myometrium. The entire invaded myometrium and the entire placenta will be removed. The uterus will repair itself in one or two layers. Intrauterine balloon tamponade will be used if indicated

10. Carry out the prospective collection of all clinical variables during surgery.

The objective measurement of the operative sac is the variable of greatest interest in a possible controlled clinical trial and requires special description since its correct measurement is basic for the analysis of results in both arms of the feasibility study and for the planning of a subsequent study.

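### The near-miss composite contains a hysterectomy item in a trial that assigns hysterectomy, so its by-arm percentage can depend partly on allocation

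*Combined protocol and SAP*

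**What the plan says.** The Synopsis and section 8.2 list as a secondary endpoint "Compliance with at least one WHO Near Miss criterion (See Appendix 1"). Section 15 defines the variable as yes/no, and Table 4 gives its percentage in total and by arm. Among the management-based criteria, Appendix 1 lists "Hysterectomy following infection or haemorrhage", with no definition of haemorrhage and no exclusion attached.

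Section 9.11 says of the hysterectomy group: "In this arm of the study, hysterectomy will be performed in 100% of patients". The sequence there is delivery, uterotonics and gentle traction, and then: "The absence of spontaneous separation of the placenta will confirm the diagnosis of PAS, the patient will undergo hysterectomy". For the resection group, section 9.3 says: "Partial myometrial resection may not be feasible in some cases and the patient will receive a hysterectomy".

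On timing, section 10.2.2 places near miss at the immediate postoperative assessment, where "each of the secondary outcomes described will be evaluated: Maternal death, Presence of Near Miss criteria" and others. The section 9.10 flowchart marks it from the first follow-up visit onward. No section says whether a hysterectomy at the index operation, assigned or by conversion, meets the item.

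**The concern.** A composite severe-morbidity endpoint should count what happened to the woman, not which operation she was allocated. Here one qualifying item is the control treatment itself, subject only to the word *following*. Two readings are open, and they can pull in opposite directions:

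- If an assigned hysterectomy preceded by intraoperative bleeding counts, women in the hysterectomy arm can qualify through an operation they would have had anyway.
- If assigned hysterectomies are treated as planned and only haemorrhage-driven conversions count, the item can be met at the index operation in the resection arm alone.

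Three centres could read the item differently in an open-label study. The same women would then give different by-arm percentages. Section 3 says that the clinical data from both arms are meant to help plan the definitive trial, so a distorted near-miss row could mislead that planning.

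**Working it through.** **Plan figures.** Section 9.6 gives 36 + 12 + 12 = 60 women. Allocation is 1:1 (section 9.12), so about 30 per arm if all 60 are analysed. The plan states no near-miss rate and made no power calculation, so there is no plan figure for this endpoint to reproduce.

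**Inputs.**
- Conversion rate c = 1 − uterine preservation. Section 2 cites preservation of 81% in an experienced series and 9% to 42% in centres new to the technique, so c = 0.19, 0.58 and 0.91. These are background figures, not assumptions made for the three participating centres.
- p, the share of women meeting any other criterion, taken as 0.40 and equal in both arms. This is an assumption, borrowed from the expected frequency above 40% in section 12.2 for more than 4 red-cell units, which in whole units is the Appendix 1 criterion of at least 5.
- h, the share of index hysterectomies judged to follow haemorrhage, and o, the share of those women who already meet another criterion. Both are assumed and set equal across arms. Independence gives o = p. In the hysterectomy arm o cannot exceed p/h.

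**Formulas.**
- All index hysterectomies after haemorrhage count: gap (hysterectomy minus resection) = h(1 − o)(1 − c).
- Only conversions count: gap (resection minus hysterectomy) = h(1 − o)c.
- Neither counts: the index operation adds 0.

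**Results**, in percentage points for c = 0.19 / 0.58 / 0.91:

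| h | o | All count, against hysterectomy | Conversions only, against resection |
|---|---|---|---|
| 1 | 0.4 | 48.6 / 25.2 / 5.4 | 11.4 / 34.8 / 54.6 |
| 0.5 | 0.4 | 24.3 / 12.6 / 2.7 | 5.7 / 17.4 / 27.3 |
| 0.25 | 0.4 | 12.2 / 6.3 / 1.4 | 2.9 / 8.7 / 13.7 |
| 0.5 | 0.8 | 8.1 / 4.2 / 0.9 | 1.9 / 5.8 / 9.1 |
| 0.25 | 1 | 0 / 0 / 0 | 0 / 0 / 0 |

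Example for row two: 0.5 × 0.6 × 0.81 = 0.243, and 0.5 × 0.6 × 0.19 = 0.057. In row four the largest gap is 0.091 × 30 = 2.7 women of 30. The first row is an extreme: it makes the hysterectomy arm 100% near miss by construction, 1 − (1 − 0.4)(1 − 1) = 1.

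**Direction.** If h differs between arms, the gap when all count is (1 − o)(h_H − c·h_R), where h_H and h_R are the shares in the hysterectomy and resection arms. With h_H = 0.25, h_R = 0.5, c = 0.58 and o = 0.4 it is 0.6 × (0.25 − 0.29) = −0.024, about 2 points against resection. Even that counting choice does not fix the sign.

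**A partial exclusion.** Dropping only index hysterectomies leaves later ones. Those are possible only in women whose uterus was preserved, a share 1 − c of the resection arm and none of the hysterectomy arm as planned. The item would still depend on allocation. The documents give no rate for later hysterectomy, so this residue cannot be sized.

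**The case against.** The strongest reply is that the plain wording already excludes both kinds. Women must enter the operating room without active bleeding (section 9.5.1). Appendix 5 tells the surgeon, "before performing hysterotomy (opening the uterus), confirm the presence of clinical signs of PAS on the anterior surface of the uterus", so the assigned operation follows allocation, confirmed signs and non-separation of the placenta. Section 9.3 describes conversion as a matter of feasibility and says that attempting resection does not increase bleeding risk. Near miss is assessed postoperatively.

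This makes counting assigned hysterectomies less likely, but it does not close the question. Bleeding can occur between hysterotomy and removal of the uterus, and Appendix 2 accepts heavy bleeding on attempted placental removal as one sign of confirmed accreta. Bladder and ureteral injury sit in the same postoperative list, so being listed there does not exclude intraoperative events. Section 9.11 assesses extreme maternal morbidity "From the admission of the patient to the obstetric care unit until the end of the study follow-up process", though under a national surveillance protocol. Appendix 1 excludes ventilation related to anaesthesia but says nothing comparable for an assigned hysterectomy.

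Other objections stand in part. The 58% and 91% conversion figures come from centres new to the technique, whereas section 14 says that both operations are routine in the participating hospitals. The section 12.2 frequencies may serve as alert limits rather than forecasts. Haemorrhage leading to hysterectomy would often also bring shock, clotting failure or at least 5 red-cell units, which shrinks the effect.

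A reader might also infer that the individual criteria will not be stored. The documents do not show that: section 10.1 lists the criteria among recorded data and the CRF is not shown. The operation assigned and the operation performed are both variables in section 15, so conversions can be identified. What section 15 lacks is the reason for conversion and the criteria met.

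**Conclusion.** The point holds as a limited one. With this item in the composite, the by-arm near-miss percentage can depend partly on allocation. Size and direction cannot be determined from the documents. The illustrative range runs from 0 to about 55 points in either direction, entirely on assumed h, o and p and on preservation rates from the background literature. With heavy overlap it is at most about 3 women of 30, and it is zero if neither kind of hysterectomy counts or if these women all meet another criterion anyway.

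A reader might infer that the hysterectomy arm must show 100% near miss, or that a gap near 49 points is to be expected. Neither is supported. Both need every assigned hysterectomy to be judged as following haemorrhage, which entry without active bleeding and confirmation before hysterotomy make unlikely.

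Only one descriptive secondary endpoint is affected. No primary feasibility outcome or sample size changes, no efficacy test is planned, and section 2 proposes bleeding volume as the primary outcome of the definitive trial. The correction is worth making because it is cheap and the row could otherwise be misread in planning.

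**What to change.** In section 8.2, section 15 and Table 4, report near miss by arm in two lines:

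- (a) the WHO composite as listed in Appendix 1;
- (b) the composite with the hysterectomy item removed entirely in both arms, at the index operation and later. Use (b) for any comparison between arms.

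Record which Appendix 1 criteria each woman met, so that section 15 matches section 10.1. Report conversions with their reason, and later hysterectomies, as separate Table 4 rows.

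The cost is one counting sentence, item-level entry in the CRF and three extra table rows (line (b), conversions with reason, later hysterectomies). No extra patients or visits are needed, and no clinical rule changes. The downside is that line (b) departs from the WHO definition and omits haemorrhage-driven hysterectomy, which is real morbidity. That morbidity stays visible in line (a) and the separate rows.
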